4.7.2. Definition of Baseline

The baseline value for 6MWD is the average of all walks prior to randomization.

Otherwise, for efficacy analyses the baseline value is defined as the last evaluation prior to randomization and for safety analyses, the baseline value is defined as the last evaluation prior to the first administration of study drug.

For ECG analyses, baseline is defined as the mean of triplicate assessments prior to the first administration of study drug. All available observations will be used in determining baseline, i.e. if there are less than 3 observations, the available observations will be used in determining the mean.

4.7.3. Definition of End of Treatment

The Main Study End of Treatment value will be defined as the Week 24 value, either scheduled or windowed per [Table 6](#).

5. ANALYSIS POPULATIONS

Table 8 defines the analysis populations to be used.

Table 8: Analysis Sets

Analysis Sets	Description
Screened	All subjects who sign the informed consent form (ICF).
Safety	All subjects who receive any amount of study drug. Treatment assignment will be based on the treatment actually received.
Intent-to-Treat (ITT)	All subjects randomized into any one of treatment groups. Treatment assignment will be based on the randomized treatment.
Modified Intent-to-Treat (mITT)	All ITT population subjects with an evaluable baseline and at least 1 post baseline PVR assessment. Treatment assignment will be based on the randomized treatment.
Per Protocol (PP)	All mITT subjects who have completed treatment with $\geq 80\%$ treatment compliance (actual, see definition in Section 8.1) without any major protocol deviations,. Treatment assignment will be based on the treatment actually received.
Treatment Completer	All mITT subjects who complete 24 weeks of treatment with no dose reductions or dose interruptions. Treatment assignment will be based on the randomized treatment. Sensitivity analyses may be conducted based on the treatment actually received. No missing data will be imputed for these analyses. Any substantial differences between conclusions based on the ITT, mITT and the completers' populations will be investigated.

6. STUDY POPULATION

6.1. Subject Disposition

Subject disposition will be summarized for the Screened population by treatment group, including Total Rodatristat ethyl and Overall. The summary will include:

- Number of subjects screened.
- Number of screen failures, i.e., screened but not randomized, with reasons for screen failure. The denominator for percentage of screen failures will be the number of subjects screened. The denominator for percentages for reasons for screen failures will be the number of screen failures.
- Number of subjects randomized (ITT population). The denominator for percentage of randomized subjects will be the number of subjects screened.

- Number randomized and not treated. The denominator for percentage of randomized and not treated subjects will be the number of subjects randomized.
- Number of subjects treated (Safety population). The denominator for percentage of treated subjects will be the number of subjects randomized.
- Number subjects in each analysis set. The denominator for percentage in each analysis set will be the number of randomized subjects (ITT population).
- Number who discontinued treatment early and reason(s) for discontinuation of treatment. The denominator for percentages will be the number of randomized subjects (ITT population).
- Number who discontinued from the main study prior to completing the study and reason(s) for discontinuation. The denominator for percentages will be the number of randomized subjects (ITT population).

The number and percentage of subjects randomized by geographical region and site will be presented by treatment group, including Total Rodatristat ethyl and Overall, for the ITT population.

A summary table will be produced of the randomization stratification factors and the combined stratum groups.

- Number of Background PAH therapies: 1, 2, or 3
- Selexipag Use: Yes, No
- Stratum Group 1: 1 Background PAH Therapy, Selexipag Use
- Stratum Group 2: 2 Background PAH Therapies, Selexipag Use
- Stratum Group 3: 3 Background PAH Therapies, Selexipag Use
- Stratum Group 4: 1 Background PAH Therapy, No Selexipag Use
- Stratum Group 5: 2 Background PAH Therapies, No Selexipag Use
- Stratum Group 6: 3 Background PAH Therapies, No Selexipag Use

If any randomization stratum has less than 5 subjects, the pooled stratum will be used as described in [Table 9](#) below.

Table 9: Pooling of Randomization Strata

Stratum	Pooled Stratum
1 PAH Therapy excluding Selexipag	1 PAH Therapy
1 PAH Therapy including Selexipag	1 PAH Therapy
2 PAH Therapies excluding Selexipag	2 PAH Therapies
2 PAH Therapies including Selexipag	2 PAH Therapies
3 PAH Therapies excluding Selexipag	3 PAH Therapies

Stratum	Pooled Stratum
3 PAH Therapies including Selexipag	3 PAH Therapies

In addition, in case the site accidentally stratified a subject using the wrong stratification value, the derived stratification value reported in the eCRF data versus the one the site entered in the IRT during randomization process will be presented separately.

A by-subject data listing of study disposition information including the reasons for treatment and/or study termination will be presented for the Screened population. Also by-subject listings of informed consent and eligibility criteria details will be presented. A by-subject data listing including the reasons for exclusion from each analysis population will be presented.

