4. STUDY DESIGN

4.1. Overall Design

This study will compare the efficacy, safety, and tolerability of 2 dosing regimens of rodatristat ethyl to placebo in patients with PAH over a 24-week treatment period. Investigational product (IP) will be administered on the background of stable PAH therapy.

Protocol RVT-1201-2002

Effective: 19JAN2022

Approximately ninety (90) patients will be enrolled. Patients will be randomized 1:1:1 to placebo, 300 mg BID, or 600 mg BID of rodatristat ethyl.

Eligible patients will be stratified based on the number of background PAH therapies they are receiving (1 vs 2 vs 3) and selexipag use (Yes/No). The number of patients who are on a prostanoid infusion will be capped at 50% of the total enrolled. The number of patients who are receiving selexipag will be capped at 20% of the total enrolled.

The study will consist of a Screening Period (up to 28 days in duration), a Baseline Period (Day 1), a 24-week Treatment Period (Main Study), and for patients that early terminate or do not enroll an Open-Label Extension (OLE), and a 4-week Follow-Up Period (approximately 4 weeks after the last dose), for a total study duration of 32 weeks.

Patients who complete the Main Study will have the option to enroll into an OLE and continue to receive rodatristat ethyl (those randomized to placebo will be re-randomized 1:1 to receive rodatristat ethyl 300 mg BID or 600 mg BID) for 6.5 years, until the Investigator or patient chooses to stop the IP, any stopping criteria in the Main Study are met, IP becomes commercially available, or the Sponsor stops the study for lack of efficacy or a safety signal (whichever preceding criteria comes first). In no case will a patient be allowed to exceed 10 years of exposure unless the product is approved for a chronic indication.

All participating patients will be required to be on a stable background therapy for PAH with mono, dual or triple combination therapy (which may include currently approved prostanoid therapies) at the time of Screening. All patients will maintain their standard of care (SOC) regimen at entry for the duration of the study. Refer to Section 6.6.2 for more details.

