6.6.1. Rodatristat-Drug Interaction Potential

In vitro experiments and in silico modeling to evaluate the drug-drug interaction potential of rodatristat ethyl and rodatristat have not identified any moderate or high risks for potential drug-drug interactions (IB, 2020). There is the potential for weak interactions with substrates of the drug metabolizing enzymes cytochrome P450 (CYP)2C8 and CYP3A, and drug transporters P-glycoprotein (P-gp) or organic anion-transporting polypeptide (OATP).

Selexipag, and active metabolite ACT-333679, are substrates of CYP2C8 and preliminary data from a selexipag-rodatristat clinical interaction study in healthy subjects are available. In that study, steady-state rodatristat ethyl 600 mg BID coadministered with single-dose selexipag 400 µg increased selexipag AUC 1.18-fold and reduced ACT-333679 AUC by 40.5%. These data suggest induction of CYP2C8 by rodatristat ethyl/rodatristat. The magnitude of this interaction in PAH patients, and the clinical relevance of these changes in exposure are unknown. PK samples for assessment of selexipag and ACT-333679 trough concentration at baseline and Week 4, in addition to safety and efficacy data, will be collected in this study to further investigate this finding. In the same study, a single-dose of selexipag 400 µg had no relevant impact on the exposure of rodatristat ethyl or rodatristat.

Preliminary safety data from the study show a total of 33 TEAEs-in 8 subjects during the study. There were no SAEs or deaths. Gastrointestinal (GI) TEAEs were the most frequently reported TEAEs over all three periods with 25 GI TEAEs occurring in 6 subjects. All TEAEs were mild to moderate with the exception of one TEAE in one subject of serious diarrhea on Day 6. This same subject was the only subject discontinued from the study. This subject was discontinued by the Investigator due to prolonged GI TEAEs (nausea, vomiting, stomachache, diarrhea) during the rodatristat ethyl alone dosing period (Days 5-9). Nausea was the only TEAE reported in 2 or more subjects when selexipag was given alone. Diarrhea, headache, nausea and stomachache were reported (in \geq 2 subjects) at approximately the same frequency during both rodatristat ethyl alone period and the selexipag and rodatristat ethyl coadministration period. There were no changes in laboratory parameters, vital signs, or ECGs of clinical significance.

No concomitant medications based on these in vitro and clinical findings are prohibited.

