2.2.3. Treatment Assignment, Blinding, and Randomization Methodology

This is a double blind study, with an open label extension (covered under a separate SAP). The Sponsor, Investigator, subject, and study site personnel will be blinded to all treatment group assignments. The Investigator will have the ability, in the IRT system, to unblind a subject, and the decision will reside solely with the Investigator. Prior to unblinding, if safety allows, the Investigator should contact the Medical Monitor to discuss the reasons for unblinding.

Eligible subjects will be stratified during the randomization process based on the number of background PAH therapies they are receiving (1, 2 or 3) and selexipag use. The number of subjects who are receiving a prostanoid infusion will be capped at 50% of the total number of subjects enrolled. The number of subjects who are receiving selexipag will be capped at 20% of the total number of subjects enrolled. Subjects will be randomized 1:1:1 to placebo, 300 mg BID, or 600 mg BID of rodatristat ethyl using an interactive randomization system.

At the time of Screening for entry into the OLE, all subjects will be re-randomized to receive either 300 mg BID or 600 mg BID rodatristat ethyl in an open-label fashion. Subjects will not know what they received in the Main Study until all subjects have completed the Main Study and the database is locked.

At the time of randomization, in the Main Study, subjects will be assigned a randomization number. Once this number has been assigned, it cannot be reused/reassigned.

Emergency unblinding procedures are outlined in section 6.4 of the study protocol and in the unblinding plan.

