3. SAMPLE SIZE JUSTIFICATION

The sample size for this study was not based on a formal hypothesis testing. It is expected that 30 evaluable subjects per arm will provide sufficient data to assess safety and efficacy. Power calculations were conducted to examine the probability of detecting a difference among treatment groups for the percentage change of PVR from baseline.

A sample size of 90 subjects with 30 subjects to be randomized into 1 of the 3 treatment arms in a 1:1:1 randomization is planned. A sample size of 30 subjects per arm will provide at least 80% power at a significance level of 0.05 (2-sided hypothesis) to detect a treatment difference of 0.75 times of standard deviation (SD) in the percentage change from baseline of PVR from baseline between an active arm and the placebo arm. If the SD for PVR percent change is 24%, the study has 80% power to detect a difference of 18% between an active arm and the placebo arm.

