7.2. Primary Efficacy Analysis

The primary efficacy analysis will test the following hypothesis:

- H_0 : The mean change from baseline in PVR at Week 24 is equal between placebo and rodatristat ethyl.
- H_1 : The mean change from baseline in PVR at Week 24 is different between placebo and rodatristat ethyl.

In cases of missing data occurring at Week 24, missing data handling rules are specified in [Section 7.1.2](#).

Percent change from baseline in PVR at Week 24 will be analyzed using an analysis of covariance (ANCOVA) model with terms of treatment, randomization strata and baseline PVR. Estimates of least-square (LS) means, standard errors (StdErr), and 95% CIs will be presented by treatment group. In addition, the LS mean difference comparisons between each active dose and placebo, the StdErr of the difference, and 95% CI of the difference will be presented.

In order to control the Type 1 error rate, the comparisons between each active arm and the placebo arm will be tested using the Hochberg approach, where the two p-values (600 mg vs placebo and 300 mg vs placebo) will be ordered largest to smallest as $p(1) > p(2)$.

1. If $p(1) < 0.05$ then reject both null hypotheses.
2. If $p(1) > 0.05$, but $p(2) < 0.025$, then reject the null hypothesis associated with $p(2)$.

Assumptions for the ANCOVA will be checked, and if not satisfied, parametric analyses will be corroborated with appropriate nonparametric analyses, such as the Wilcoxon rank sum test stratified by randomization strata. The Hodges-Lehmann estimation of location shift and confidence interval will be produced. If the model residuals are not normally distributed, ANCOVA analysis based on ranked data will be performed.

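### The sparse-stratum rule in SAP 6.1 will probably be triggered, and it pools away selexipag use, a randomization factor, from the models that adjust for randomization strata

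*SAP*

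**What the plan says.** Randomization is stratified by number of background PAH therapies (1, 2 or 3) and selexipag use (yes/no), which gives six strata (Protocol 4.1 and 6.4; SAP 2.2.3). Protocol 4.1 adds: "The number of patients who are receiving selexipag will be capped at 20% of the total enrolled".

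SAP 6.1, under Subject Disposition, sets the pooling rule: "If any randomization stratum has less than 5 subjects, the pooled stratum will be used". Table 9 maps each selexipag stratum and the non-selexipag stratum with the same number of therapies to one pooled stratum. Three strata remain, for 1, 2 and 3 therapies.

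The primary analysis in SAP 7.2 is an "analysis of covariance (ANCOVA) model with terms of treatment, randomization strata and baseline PVR". The WHO FC ordinal logistic model (7.3.1), the NT-proBNP MMRM (7.3.3) and the log-rank and Cox analyses (7.4.2) also refer to randomization strata. The 6MWD aligned-rank test (7.3.2), the CMH test (7.3.1.1) and the imputation model (7.1.2.1) refer instead to the stratification factors. Section 7 does not mention Table 9.

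**The concern.** The cap makes the selexipag cells small by design, so a rule that acts when any cell is below 5 is likely to act. When it does, Table 9 removes the selexipag split and keeps number of therapies. Selexipag was added as a stratification factor in Protocol Amendment 1 because of an interaction study, in which rodatristat ethyl "increased selexipag AUC 1.18-fold and reduced ACT-333679 AUC by 40.5" per cent (Protocol 6.6.1).

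At stake are agreement between the analysis and the randomization, some precision in the primary comparison, and a uniquely specified primary model. The SAP leaves three things open: whether one small cell collapses all three pairs or only its own, in which population the 5 are counted, and which analyses use the pooled variable.

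**Working it through.** **The plan's own figure.** SAP 3 plans 30 per arm, two-sided 0.05, and states: "If the SD for PVR percent change is 24%, the study has 80% power to detect a difference of 18" per cent. The standardized effect is 18/24 = 0.75. The noncentrality is 0.75 × √(30/2) = 2.905. With 58 df the critical value is 2.002 and the power is 81.5%, which agrees with at least 80%.

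**Probability of the trigger.** The cap allows 0.20 × 90 = 18 users over three cells. No selexipag cell is below 5 only if all three hold at least 5, which needs 3 × 5 = 15 users. With 14 or fewer the trigger is certain. Above that, P(trigger) = 1 − P(all three cells ≥ 5), from the exact multinomial. The documents give no split over 1/2/3 therapies, so the splits are assumptions.

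| Users | 33/33/33 | 20/40/40 | 15/35/50 | 10/30/60 | 5/35/60 |
|---|---|---|---|---|---|
| ≤14 | 100% | 100% | 100% | 100% | 100% |
| 15 | 94.7% | 97.5% | 99.1% | 99.9% | >99.9% |
| 16 | 85.9% | 93.2% | 97.5% | 99.6% | >99.9% |
| 18 | 64.3% | 82.1% | 93.0% | 98.8% | 99.9% |

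The even split is the most favourable case. A small non-selexipag cell can only raise these figures.

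**Global or pairwise pooling.** If any small cell switches the analysis to Table 9, selexipag leaves the model altogether. If only the affected pair is pooled, selexipag usually survives somewhere. Three cells of at most 4 hold at most 12 users, so with 13 or more at least one selexipag cell reaches 5. Its pair then stays separate unless its non-selexipag cell is small. With exactly 12 users, all three selexipag cells fall below 5 with probability 0.0% to 6.5% over these splits.

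**Cost in precision.** Residual df with 90 patients, three arms and baseline PVR:
- pooled strata: 90 − 3 − 1 − 2 = 84
- two main effects: 90 − 3 − 1 − 3 = 83
- six strata: 90 − 3 − 1 − 5 = 81

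Take 24% as the residual SD of the pooled-strata model (assumption). Suppose users (20%) differ from non-users by g residual SD (assumption). The share of variance left unexplained by dropping selexipag is R² = 0.16g²/(1 + 0.16g²), where 0.16 = 0.2 × 0.8. Keeping the factor raises the noncentrality to 2.905/√(1 − R²).

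| g | R² | Power, pooled (84 df) | Power, two main effects (83 df) |
|---|---|---|---|
| 0 | 0 | 81.90% | 81.89% |
| 0.25 | 1.0% | 81.9% | 82.3% |
| 0.5 | 3.8% | 81.9% | 83.3% |
| 1.0 | 13.8% | 81.9% | 87.1% |

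This is power per comparison at 0.05. With fewer users the gain shrinks. At 14 users, R² is 3.2% for g = 0.5 and 11.6% for g = 1.0.

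**The case against.** Pooling sparse cells by a pre-specified count is ordinary practice, and several stronger readings go beyond the documents.

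- *The trigger is almost certain.* A reader might infer this, but it is established only at 14 or fewer users. At 18 it rests on an unseen mix. Nor is 18 exact, since enrolment is approximate and replacements are allowed. With 20 users (100 enrolled, an assumption) the probability is 44% for an even split and 70% for 20/40/40.
- *Selexipag is lost from every stratified test.* This does not follow. The rule sits under Subject Disposition, section 7 never cites Table 9, and the 6MWD, CMH and imputation text names the stratification factors.
- *The comparison is biased or underpowered.* Neither holds. Omitting a factor balanced by stratified randomization costs precision only, and 81.9% still meets the stated 80%.
- *The plan ignores the interaction.* It does not: there are the cap, selexipag trough sampling and a selexipag subgroup (SAP 7.1.7). A selexipag main effect would not test or adjust for a treatment-by-selexipag interaction anyway.

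All of this stands and limits the point. One qualification concerns the subgroup. It requires at least 5 patients per treatment group in each category, hence at least 15 users. With 14 or fewer users, where pooling is certain, the subgroup is not shown either. When it is shown, it uses observed data only and does not adjust the primary comparison.

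**Conclusion.** The point holds as a specification gap with a modest cost in precision. The trigger is likely under the documents' own cap. On the more natural reading of a rule that acts on any small stratum, selexipag use then leaves the PVR ANCOVA, the WHO FC ordinal logistic model, the NT-proBNP MMRM, and the log-rank and Cox analyses. On the pairwise reading it leaves only the affected pair.

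The loss ranges from nil to about 5 points of power per comparison (81.9% against 87.1% at a 1.0 SD difference). It depends entirely on an assumed difference in PVR response between users and non-users, for which the documents give no figure. The case for changing the plan rests on how little the change costs and on having one defined primary model before unblinding.

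**What to change.** In the ANCOVA, MMRM and ordinal logistic models, replace the combined or pooled stratum with two main-effect factors: number of background therapies (1, 2, 3) and selexipag use (yes/no). This needs no pooling rule and follows the factors used in randomization. It costs 1 df against the pooled strata, which is 81.89% against 81.90% power if selexipag explains nothing. Against the six-cell stratum it gives up only the therapies-by-selexipag interaction terms.

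For the analyses that need strata (aligned-rank, CMH, and log-rank with its stratified Cox model), state in section 7 whether Table 9 applies, whether pooling is global or pairwise, and in which population the 5 are counted. The direction of pooling there is a choice: merging across number of therapies within selexipag users would keep selexipag but give up number of therapies among those users.

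The change takes a few lines of SAP text and no new data. It should be made before unblinding.

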6.2. Demographics and Baseline Characteristics

Demographic variables will include the following:

- Age at informed consent including the subgroup of <65 years, ≥ 65 years
- Sex
- Race
- Ethnicity

Other baseline characteristics will include the following:

- Weight (kg)
- BMI (kg/m^2) including the following subgroup: $<18 \text{ kg}/\text{m}^2$, 18 to $<30 \text{ kg}/\text{m}^2$, $\geq 30 \text{ kg}/\text{m}^2$

PAH baseline characteristics will be summarized and listed separately and include the below parameters:

- Duration since PAH Diagnosis (years)
- PAH Classification (IPAH, HPAH, drug or toxin, PAH associated with connective tissue disease, PAH associated with congenital systemic pulmonary shunt, PAH associated with HIV)
- Number of PAH therapies
- WHO FC (I, II, III, IV)
- Baseline REVEAL Lite Score including the following subgroup: <6 vs ≥ 6
- Baseline 6MWD (meters)
- Baseline NT-proBNP (pg/mL)
- Baseline PVR (dynes/sec/cm⁵)
- Baseline mPAP (mmHg), Baseline PCWP (mmHg), Baseline mRAP (mmHg), Baseline Cardiac Index (L/min/m²), Cardiac Output (L/min), adjudicated values.

If date of PAH diagnosis is only partially known, i.e. the month or day is missing, it will be imputed as the closest to randomization date, where missing day is imputed as the last day of the month and missing day and month is imputed as December 31.

In addition, any subgroups specified in [Section 7.1.7](#) for the above parameters will be included in summaries. Demographics and baseline characteristics will be summarized by treatment group, including Total Rodatristat ethyl and Overall, for the ITT, mITT, Safety, PP, and Treatment Completer populations. The mITT, Safety, PP, and Treatment Completer populations will only be presented if the analysis population differs from the ITT population by more than 10% total.

All demographic and baseline characteristics data will be presented in by-subject data listings using the ITT population.

No inferential statistical comparisons will be performed.

